8.10. Biases

Selection bias

In order to minimize selection bias, the sampling strategy that was designed for the proposed study will reflect real-life clinical practice since it will capture all possible treatment settings. In addition, selection bias due to sampling and participation will be assessed by comparing characteristics of the participating versus non-participating patients and prescribers.

Information bias

At the patient level, misclassification of drug exposure has to be considered. Medical records provide detailed information on prescribed and/or dispensed medications but may not contain information on the intended duration of use (days of supply) and often do not contain information on the actual use of the medications by the patient. Thus, patients may be classified as exposed to a drug although they actually have not taken the drug. For this reason, great care will be taken to ensure the quality of the information that is abstracted, and prescribers' follow-up by clinical research associates (CRAs) will be enforced.

Missing Data

Some limitations with regard to data completeness may occur in this study, mainly related to the information captured in the patients' medical records. Measures to minimize missing data will be implemented, including:

- Ensuring that primary variables of interest are those that are routinely collected as part of real-world clinical care.
- Collecting only critical data elements (ie, variables aligned with the study objectives) to minimize site/participant burden.
- Including "not applicable"/"not done" on CRFs to differentiate these from values that are truly missing.

- CRF completion guidelines will provide consistent instructions on completion of the CRF.
- All individuals performing data abstraction from medical records will be trained on appropriate data abstraction techniques in order to minimize possible discrepancies between interpretation of the information recorded by the prescriber in the medical records and the individual performing the review and abstraction of the data.
- Missing data will be followed up on during monitoring visits.
- Checking for patterns of missing data and addressing any issues with targeted operational strategies.

8.11. Other Aspects

Not applicable.

9. PROTECTION OF HUMAN SUBJECTS

9.1. Patient Information

All parties will comply with all applicable laws, including laws regarding the implementation of organizational and technical measures to ensure protection of patient personal data. Such measures will include omitting patient names or other directly identifiable data in any reports, publications, or other disclosures, except where required by applicable laws.

The personal data will be stored at the study site in encrypted electronic and/or paper form and will be password protected or secured in a locked room to ensure that only authorized study staff have access. The study site will implement appropriate technical and organizational measures to ensure that the personal data can be recovered in the event of disaster. In the event of a potential personal data breach, the study site shall be responsible for determining whether a personal data breach has in fact occurred and, if so, providing breach notifications as required by law.

To protect the rights and freedoms of natural persons with regard to the processing of personal data, when study data are compiled for transfer to Pfizer and other authorized parties, patient names will be removed and will be replaced by a single, specific, numerical code, based on a numbering system defined by Pfizer. All other identifiable data transferred to Pfizer or other authorized parties will be identified by a single, patient-specific code. The investigator site will maintain a confidential list of patients who participated in the study, linking each patient's numerical code to his or her actual identity. In case of data transfer, Pfizer will maintain high standards of confidentiality and protection of patients' personal data consistent with the CSA and applicable privacy laws.

9.2. Patient Consent

The informed consent documents and any patient recruitment materials must be in compliance with local regulatory requirements and legal requirements, including applicable privacy laws.

The informed consent documents used during the informed consent process and any patient recruitment materials must be reviewed and approved by Pfizer, approved by the IRB/IEC before use, and available for inspection.

The investigator must ensure that each study patient, or his or her legally acceptable representative, is fully informed about the nature and objectives of the study, the sharing of data relating to the study and possible risks associated with participation, including the risks associated with the processing of the patient's personal data. The investigator further must ensure that each study patient, or his or her legally acceptable representative, is fully informed about his or her right to access and correct his or her personal data and to withdraw consent for the processing of his or her personal data.

Whenever consent is obtained from a patient's legally acceptable representative, the patient's assent (affirmative agreement) must subsequently be obtained when the patient has the capacity to provide assent, as determined by the IRB/IEC. If the investigator determines that a patient's decisional capacity is so limited that he or she cannot reasonably be consulted, then, as permitted by the IRB/IEC and consistent with local regulatory and legal requirements, the patient's assent may be waived with source documentation of the reason assent was not obtained. If the study patient does not provide his or her own consent, the source documents must record why the patient did not provide consent (eg, minor, decisionally impaired adult), how the investigator determined that the person signing the consent was the patient's legally acceptable representative, the consent signer's relationship to the study patient (eg, parent, spouse), and that the patient's assent was obtained or waived. If assent is obtained verbally, it must be documented in the source documents.

The investigator, or a person designated by the investigator, will obtain written informed consent from each patient or the patient's legally acceptable representative, before any study-specific activity is performed unless a waiver of informed consent has been granted by an IRB/IEC. The investigator will retain the original of each patient's signed consent document.

9.3. Patient Withdrawal

Patients may withdraw from the study at any time at their own request, or they may be withdrawn at any time at the discretion of the investigator or sponsor for safety, behavioral, or administrative reasons. In any circumstance, every effort should be made to document patient outcome, if applicable. The investigator would inquire about the reason for withdrawal and follow-up with the patient regarding any unresolved adverse events.

If the patient withdraws from the study, and also withdraws consent for disclosure of future information, no further evaluations should be performed, and no additional data should be collected. The sponsor may retain and continue to use any data collected before such withdrawal of consent.

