7.1. Primary Objectives

- To determine clinical outcomes including (but not limited to):
 - Proportion of patients who are progression free and alive at specific intervals (eg, 12, 18 months).
 - Proportion of patients alive 1- and 2-years post palbociclib combination initiation - depending on availability of follow-up data.

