8. RESEARCH METHODS

8.1. Study Design

This is a prospective, non-interventional (NI), multicenter study being conducted in Africa Middle East (AfME) countries. The aim is to understand palbociclib treatment patterns, clinical outcomes and QoL for patients with metastatic/locally advanced BC being treated in routine clinical practice in 7 AfME countries: Egypt, Jordan, KSA, Lebanon, Morocco, Qatar and UAE.

Approximately 200 patients from 19 centers across the 7 countries will be enrolled. The recruitment period (ie, from first patient into last patient in) will span over 18 months.

[figure not shown]
Patients will be enrolled at the time of treatment initiation with palbociclib and will be followed up over a 24-month period at time intervals per routine care, or until patient's withdrawal from the study or death (whichever comes first). Prospective data on clinical characteristics, treatment patterns, clinical outcomes and QoL will be collected ([Figure 1](#)).

Participation in this study is not intended to change the routine treatment patients receive, as determined by their prescribing physicians; all treatment decisions, type and timing of the disease monitoring are per routine clinical care, and at the discretion of treating physician and patient.

All assessments described in this protocol are performed as part of normal clinical practice or standard practice guidelines for the patient population and healthcare provider specialty in the countries where this non-interventional study is being conducted.

All assessments described in this protocol are performed as part of normal clinical practice or standard practice guidelines for the patient population and healthcare provider specialty in the countries where this non-interventional study is being conducted.

Figure 1. Study Design

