8.2. Setting

Patients with HR+/HER2- metastatic/locally advanced BC within Egypt, Jordan, KSA, Lebanon, Morocco, Qatar and UAE will be enrolled from a geographically representative population as well as from diverse treatment settings (eg, academic and community sites). Patients whose treatment decision with palbociclib combination has been made by their treating physician and meet the eligibility criteria will be invited to participate in the study in a consecutive manner and over 18 months of recruitment. Data will be collected in accordance with routine standard of care visits. Eligibility will be assessed at the date of the enrollment. Data will be collected at enrollment (time of treatment initiation), during treatment with palbociclib and after treatment with palbociclib, over a 24-month period (at time intervals per routine care). After the end of treatment with palbociclib, data related to the first immediate subsequent treatment received will be collected. Patients included in the study will be followed up until the end of the follow-up, withdrawal or death, whichever occurs first.

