Treatment completed	Palbociclib treatment characteristics (secondary endpoint)	At Palbociclib treatment discontinuation	CRF sheet: Palbociclib treatment discontinuation form	
 Yes (reason of discontinuation is "Completion of planned course of treatment"); no (other reason or censored)
Duration of Palbociclib treatment	Palbociclib treatment characteristics (secondary endpoint)	At Palbociclib treatment discontinuation	CRF sheet: Palbociclib treatment discontinuation form	
 Time (in days) from first to last day in Palbociclib treatment
Another treatment after discontinuing treatment with Palbociclib	Palbociclib treatment characteristics (secondary endpoint)	At Palbociclib treatment discontinuation	CRF sheet: Palbociclib treatment discontinuation form	
 Yes No
Reason for end of follow-up	Clinical outcomes (primary endpoint)	At last visit	CRF sheet: End of Observation/ End of Study Follow Up	
End of follow-up will be categorised as:
 
 Death Patient withdrawal Lost to follow-up End of 24-months follow-up period
Concomitant medications	Clinical characteristics (secondary endpoint)	At Palbociclib treatment initiation, At follow-up visits	CRF sheet: Concomitant Medications Form	Open field. 10 most common will be listed.
Supportive therapies	Supportive therapies (secondary endpoint)	At the initiation of Palbociclib treatment	CRF sheet: Supportive Therapies Form	The type of the supportive therapies received by the patients since the BC diagnosis. Open field. 10 most common will be listed.
Comorbidities	Clinical characteristics (secondary endpoint)	At the initiation of Palbociclib treatment	CRF sheet: Comorbidities form	Open field. 10 most common comorbidities will be listed
Proportion of progression free patients	Clinical outcomes (primary endpoint)	At the follow-up visits	CRF sheet: Tumor Assessment Form and End of follow-up	The proportion of the patients who are alive and for whom no progression of the disease has been reported.
Progression free survival (PFS)	Clinical outcomes (exploratory endpoint)	At the follow-up visits	CRF sheet: Tumor Assessment Form and End of follow-up	The time from the Palbociclib treatment initiation until the progression of the disease or death to any cause, whichever occurs first.

PFIZER CONFIDENTIAL

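### Protocol 8.1/8.2 and SAP 3.1 stop at any withdrawal although Protocol 9.3 still asks for the outcome, so usable primary-outcome data can be lost

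*Protocol*

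**What the plan says.** **Protocol 9.3** covers patients who leave at their own request and adds that "they may be withdrawn at any time at the discretion of the investigator or sponsor for safety, behavioral, or administrative reasons". The next sentence reads "In any circumstance, every effort should be made to document patient outcome, if applicable", and the investigator is to ask why the patient left. Collection stops only in a narrower case: "If the patient withdraws from the study, and also withdraws consent for disclosure of future information, no further evaluations should be performed".

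**Protocol 8.1** runs follow-up for 24 months "or until patient's withdrawal from the study or death (whichever comes first"). **Protocol 8.2** says "Patients included in the study will be followed up until the end of the follow-up, withdrawal or death, whichever occurs first". Neither makes an exception for patients who still allow disclosure.

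**SAP 2.1** ends follow-up at the end of palbociclib treatment, progression or withdrawal. **SAP 3.1** lists withdrawal among the censoring events.

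**SAP Annex 1, Table 3**, under "End of follow-up will be categorised as", gives four entries: death, patient withdrawal, loss to follow-up and completion of 24 months.

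**Primary outcomes.** Protocol 7.1 names "Proportion of patients alive 1- and 2-years post palbociclib combination initiation" and the proportion progression-free and alive at set intervals. SAP 6.1 estimates the progression-free proportion by Kaplan-Meier. It takes survival as those alive at 1 and 2 years divided by all who started. Protocol 8.7 and SAP 5 rule out imputation.

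**The concern.** This is an observational study. The physician chooses treatment, and the clinical data are entered from existing medical records. A decision by the investigator or sponsor to withdraw a patient from the study does not stop the chart, and it does not withdraw the patient's permission to use it. Yet a site that follows 8.1 and 8.2 would stop entering data. Anything gathered under 9.3 would fall after the SAP's censoring date.

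The outcomes at risk are the primary ones. A patient withdrawn at month 5 may have no recorded status at 1 or 2 years, even though the hospital knows it. If withdrawal is related to prognosis, that missingness is informative. Without a category for exits decided by investigator or sponsor, the planned tables cannot show how many there were.

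**Working it through.** **Step 1. Set the rules side by side by type of exit.**

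| Exit | Protocol 9.3 | Protocol 8.1/8.2 | SAP 3.1 | SAP Annex 1 category |
|---|---|---|---|---|
| Patient leaves and withdraws disclosure consent | No more data | Follow-up ends | Censored | Patient withdrawal |
| Patient leaves, disclosure consent kept | Outcome to be sought | Follow-up ends | Censored | Patient withdrawal |
| Investigator or sponsor withdraws the patient | Outcome to be sought | Follow-up ends | Censored | None |

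The sections agree only in the first row. In the other two, 9.3 permits and requests data that the other sections do not collect or use. Section 9.3 gives no method, time point or horizon for its request.

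**Step 2. Find which estimate moves, and which way.**

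- *Progression-free proportion.* SAP 6.1 gives no withdrawal rule of its own, so 3.1 applies. Kaplan-Meier assumes that censored patients have the same later risk as those who remain. If their prognosis is worse, the estimate is too high.
- *Patients alive at 1 and 2 years.* SAP 6.1 divides by all starters and does not say how unknown status is counted. If it is counted as not alive, the estimate is too low.

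**Step 3. Illustrate the size.** The plan states no withdrawal rate, so there is no figure of its own to reproduce.

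Inputs from the documents:
- N = 200 (Protocol 8.1).
- 12-month survival S of 95.3% or 87.9%, and 12-month progression-free proportion of 75.5% (Protocol 6.1, earlier US studies).

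Assumptions:
- A share w of 5%, 10% or 20% withdraws early with unknown status.
- Withdrawn patients do d = 10, 20 or 30 points worse than the rest.

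*Kaplan-Meier.* Reported is about S_r, the proportion among those who remain. True = (1 − w)·S_r + w·(S_r − d). Excess = w·d, whatever S_r is.

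| w | d = 10 | d = 20 | d = 30 |
|---|---|---|---|
| 5% | 0.5 | 1.0 | 1.5 |
| 10% | 1.0 | 2.0 | 3.0 |
| 20% | 2.0 | 4.0 | 6.0 |

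These are percentage points. The 95% half-width at 75.5% with N = 200 is 1.96·√(0.755·0.245/200) = 6.0 points.

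*Ratio over all starters.* With S among patients of known status, the truth lies between (1 − w)·S and (1 − w)·S + w.

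| w | Unknown (n) | S = 95.3% | S = 87.9% |
|---|---|---|---|
| 5% | 10 | 90.5–95.5% | 83.5–88.5% |
| 10% | 20 | 85.8–95.8% | 79.1–89.1% |
| 20% | 40 | 76.2–96.2% | 70.3–90.3% |

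Counting unknowns as not alive reports the lower bound. The shortfall is w times the withdrawn patients' true survival. At w = 10% and d = 20 points:
- S = 95.3%: 0.10 × 0.753 = 7.5 points, against a 95% half-width of 2.9.
- S = 87.9%: 0.10 × 0.679 = 6.8 points, against a 95% half-width of 4.5.

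**The case against.** **The sections can coexist.** Sections 8.1 and 8.2 may set only when routine follow-up ends, with 9.3 setting a duty at exit. This stands in part, since 9.3 does ask for the outcome. But the duty has no method or horizon, and SAP 3.1 censors at withdrawal. Only the exploratory PFS rule in SAP 6.3, which censors at the last record entry, could take later data; TTP in the same section censors at withdrawal.

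**Patients with toxicity or poor adherence.** A reader might infer that the safety and behaviour grounds in 9.3 will remove these patients. The documents do not say so. SAP Annex 1 lists both as reasons for stopping palbociclib, separately from reasons for ending follow-up, and Protocol 8.2 plans data collection after treatment. Neither is a study objective, and Protocol 10 states that collecting adverse events is outside the protocol.

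**Overstated survival.** A reader might also infer that the survival proportions will be too high. Protocol 8.7 and SAP 6 mention Kaplan-Meier for death in general terms, but SAP 6.1 specifies the crude ratio, which errs the other way if unknowns count as not alive.

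**The form itself is not shown.** Annex 1 gives reporting categories; the eCRF is not in the documents. How a site would code an exit decided by the investigator is therefore unknown. The gap in the SAP list remains.

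**Other rules also lose outcomes.** SAP 2.1 and 3.1 stop at the end of palbociclib treatment, and Protocol Table 2 marks no clinical outcomes after treatment. This stands: changing 9.3 alone would achieve little.

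**Conclusion.** The inconsistency is real and should be resolved. Protocol 9.3 permits and requests outcome data that Protocol 8.1/8.2 and SAP 3.1, followed literally, do not collect or analyse, and the SAP list omits one route out of the study. Primary-outcome data can be lost without need.

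The direction of error differs by estimate. If withdrawn patients do worse, the Kaplan-Meier progression-free proportion is too high. If unknown status is counted as not alive, the survival ratio is too low. The size cannot be determined. With 10% early withdrawal, the assumed inputs give 1 to 3 points for the first, which is within sampling error. For the second they give about 7 points at a 20-point difference, which exceeds it. Both figures rest on the assumed rate, the assumed difference and withdrawal before most events. With few withdrawals, both are small.

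**What to change.** - Reconcile Protocol 8.1/8.2, SAP 2.1 and SAP 3.1 with Protocol 9.3. Unless disclosure consent is withdrawn, take vital status and any recorded progression from the chart up to 24 months, and use them in the primary analyses. Protocol Table 2 should then show this collection.
- State that stopping palbociclib is not withdrawal from the study.
- Add two items to the end-of-follow-up form and SAP Annex 1: withdrawn by investigator or sponsor, with the reason; and disclosure consent withdrawn, yes or no.
- State in SAP 6.1 how remaining unknown vital status enters the survival proportion, for example by a Kaplan-Meier estimate censored at the date last known alive.

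Deleting the safety and behaviour grounds from 9.3 is optional; it matters little once outcomes are captured after exit.

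The cost is a short amendment, two eCRF fields and a chart look-up for what should be few patients. Patients keep the right to withdraw and to bar further use of their data.

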9.4. Institutional Review Board (IRB)/Independent Ethics Committee (IEC)

It is the responsibility of the investigator to have prospective approval of the study protocol, protocol amendments, and informed consent forms, and other relevant documents, (eg, recruitment advertisements), if applicable, from the IRB/IEC. All correspondence with the IRB/IEC should be retained by the investigator. Copies of IRB/IEC approvals should be forwarded to Pfizer.

9.5. Ethical Conduct of the Study

The observational study will be conducted in accordance with legal and regulatory requirements, as well as with scientific purpose, value and rigor and follow generally accepted research practices described in Good Pharmacoepidemiological Practice (GPP) issued by the International Society for Pharmacoepidemiology (ISPE), Declaration of Helsinki and its amendments, and any applicable national guidelines.

10. MANAGEMENT AND REPORTING OF ADVERSE EVENTS/ADVERSE REACTIONS

Collecting Adverse Events is not a part of this protocol.

[Table 4](#) summarizes the requirements for reporting safety events on the non-interventional study (NIS). NIS adverse event monitoring (AEM) Report Form to Pfizer Drug Safety Unit. These requirements are delineated for 3 types of events: (1) serious adverse events (SAEs); (2) non-serious adverse events (AEs) (as applicable); and (3) scenarios involving drug exposure, including exposure during pregnancy, exposure during breast feeding, medication error, overdose, misuse, extravasation, and occupational exposure. These events are defined in [Section 10.4](#) “Definitions of safety events”.

Table 4. Recording and Reporting of Safety Events

Safety event	Reported on the NIS AEM Report Form to Pfizer Safety within 24 hours of awareness
SAE	All
Non-serious AE	None
Scenarios involving exposure to a drug under study, including exposure during pregnancy, exposure during breast feeding, medication error, overdose, misuse, extravasation; lack of efficacy; and occupational exposure	All (regardless of whether associated with an AE)

For each AE, the investigator must pursue and obtain information adequate both to determine the outcome of the AE and to assess whether it meets the criteria for classification as a SAE (see [Section 10.4.2](#) "Serious adverse events").

Safety events listed in Table 4 must be reported to Pfizer within 24 hours of awareness of the event by the investigator regardless of whether the event is determined by the investigator to be related to palbociclib. In particular, if the SAE is fatal or life-threatening, notification to Pfizer must be made immediately, irrespective of the extent of available event information. This timeframe also applies to additional new (follow-up) information on previously forwarded safety event reports. In the rare situation that the investigator does not become immediately aware of the occurrence of a safety event, the investigator must report the event within 24 hours after learning of it and document the time of his/her first awareness of the events.

For safety events that are considered serious or that are identified in the far-right column of Table 4 that are reportable to Pfizer within 24 hours of awareness, the investigator is obligated to pursue and to provide any additional information to Pfizer in accordance with this 24-hour timeframe. In addition, an investigator may be requested by Pfizer to obtain specific follow-up information in an expedited fashion. This information is more detailed than that recorded on the data collection tool (eg, case report form). In general, this will include a description of the AE in sufficient detail to allow for a complete medical assessment of the case and independent determination of possible causality. Any information relevant to the event, such as concomitant medications and illnesses must be provided. In the case of a patient death, a summary of available autopsy findings must be submitted as soon as possible to Pfizer or its designated representative.

090177e19bc3ff14\Approved\Approved On: 10-Nov-2022 09:28 (GMT)

